[figure not shown]

Association between Vitamin D and The Development of Uterine Fibroids

2018.3.15

Study objectives The primary objective of this part is to assess the efficacy of supplementation with vitamin D on inhibiting the development of uterine fibroids in one year and two years. The secondary objective of this study is to evaluate the safety of supplementation with vitamin D in subjects.

Trial design This is an open-label, randomised controlled trial. After signing of informed consent, patients with vitamin D deficiency ($12 \text{ ng/ml} \leq \text{Serum 25-hydroxyvitamin D}_3 < 20 \text{ ng/ml}$) and uterine fibroids will be randomly assigned in a 1:1 ratio to intervention group A or control group B. Intervention group A will accept an oral dose of 1600 IU/day vitamin D₃ for up to 2 years. Control group B will receive 2 years follow-up. Patients with vitamin D insufficiency ($20 \text{ ng/ml} \leq \text{Serum 25-hydroxyvitamin D}_3 < 30 \text{ ng/ml}$) and uterine fibroids will be randomly assigned in a 1:1 ratio to intervention group C or control group D. Intervention group C will accept an oral dose of 800 IU/day vitamin D₃ for up to 2 years. Control group D will receive 2 years follow-up. Gynecologic ultrasound examinations will be performed every three months. The mount, location and size of the uterine fibroids will be documented (the transverse, longitudinal, and antero-posterior diameters of fibroids will be documented at each efficacy ultrasound examination for volume calculation). Percent change in volume of the total fibroids compared to baseline in different groups (baseline = last value obtained before randomization). Three perpendicular diameters (d₁, d₂, and d₃) were collected for each fibroid, and the volume of each fibroid (in cm³) was calculated with the ellipsoid formula: $4/3 * \pi * (d_1 * d_2 * d_3)/8$. For each patient, the total volume of fibroids (defined as the sum of the volumes of all the fibroids detected) was also calculated. The safety of vitamin D in subjects with uterine fibroids will be evaluated, including blood routine examination, electrolyte, hepatic and renal function, liver and urinary system ultrasound, and serum 25-hydroxyvitamin D₃. Vitamin D₃ Drops are purchased from Sinopharm star shark pharmaceutical (xiamen) co., LTD. An overview of the study design is shown in Figure 2 and Table 2.

[figure not shown]

Figure 2 flow diagram.

Table 2:time of date collection

Follow-up	1	2	3	4	5	6	7	8	9
Months	0	3	6	9	12	15	18	21	24
The form of follow-up	Out-patient								
Informed consent	X								
Medical history	X								
Physical examination	X								
Serum 25-hydroxyvitamin D ₃	X	X	X	X	X	X	X	X	X
Urine pregnancy test	X	X	X	X	X	X	X	X	X
Gynecologic ultrasound	X	X	X	X	X	X	X	X	X
Hepatic and renal function	X		X		X		X		X
Electrolyte	X		X		X		X		X
Blood routine examination	X		X		X		X		X
Liver and urinary		X			X				X
System ultrasound			X						
Side-effect assessment		X	X	X	X	X	X	X	X
Changes in menstruation		X	X	X	X	X	X	X	X
Adverse event assessment		X	X	X	X	X	X	X	X
Vitamin D receptor genotype	X								

Sample size According to a previous study, the volume of uterine fibroids was 8.2 (2.1-30.5) cm³ after the supplement of vitamin D 12 months and 11.4 (5.5-22.3) cm³ in the control group, respectively. On the basis of a 0.9 power to detect a significant difference ($\alpha=0.05$, one-sided), 320 participants will be required for the four groups and in a 1:1:1:1 ratio. Allowing for a 10% withdrawal rate, we plan to include 360 patients in the whole trial.

Inclusion criteria

1. Patients are willing to cooperate with the follow-up and sign informed consent;
2. Females aged 35-50 who are diagnosed as having uterine fibroids by transvaginal or abdominal ultrasonography;
3. The maximum average diameter of intramural myoma is $\leq 4\text{cm}$, $\geq 1\text{cm}$; The amount of myoma is less than 4;
4. Serum 25-hydroxyvitamin D₃ $< 30\text{ ng/ml}$, $\geq 12\text{ ng/ml}$.

Exclusion criteria

1. Patients with heavy menstrual bleeding ($>80.0\text{ mL}$), menstrual disorders, pelvic discomfort, infertility, or other indications for operation;

2. Patients complicated with myoma degeneration and adenomyosis that were suspected or diagnosed by ultrasound or gynecologic examination;
3. Allergic to vitamin D₃;
4. Use of sexual hormone, mifepristone, gonadotropin-releasing hormone agonist (GnRHa), or other medication which is likely to interfere with uterine fibroids within 3 months;
5. Pregnancy, lactation, postmenopause, or planned pregnancy within two years;
6. Suspected or identified as other tumors of genital tract;
7. History of osteoporosis or vitamin D deficiency taking vitamin D supplements within previous one month;
8. History of autoimmune diseases, infectious diseases (tuberculosis, AIDS), autoimmune diseases, digestive system diseases (malabsorption, crohn disease, and dysentery);
9. Alanine aminotransferase (ALT) or aspartate transaminase (AST) more than 3 times of the normal upper limit, total bilirubin (TBIL) more than 2 times of the normal upper limit;
10. Creatinine levels ≥ 1.4 mg/dL (123 μ mol/L) or creatinine clearance ≤ 50 mL/min;
11. History of malignant tumors;
12. Simultaneous participation in another clinical study with investigational medicinal product(s) or researcher thinks the subjects are not suitable for this trial.

Outcomes measures Primary outcomes: percent change in volume of the largest fibroid and total fibroids compared to baseline (baseline = last value obtained before randomization; measured by ultrasound examination). Secondary outcomes: percentage of subjects undergoing other medical or surgical treatment, hypercalcemia, urinary calculus, abnormal liver and renal function. Ultrasound examinations will be performed by a physician well experienced in gynecology. If possible, the same examiner should conduct all examinations of a subject throughout the study and the same ultrasound machine (per site) should be used throughout the study. For each subject, the most appropriate ultrasound method (transvaginal or abdominal) should be used depending on fibroids location and this method should be used consistently throughout the study.

Withdrawal Subjects must be withdrawn from the study when one of the following criteria occurs:

1. At their own request. At any time during the study and without giving reasons, a subject may decline to participate further. The subject will not suffer any disadvantages as a result;
2. In the investigator's opinion, continuation of the study treatment would be harmful to the subject's health;
3. Obvious non-compliance;
4. Lost to follow-up;
5. Pregnancy;
6. Other medical or surgical treatments of uterine fibroids.
7. Receive other medical treatments which may affect the level of serum 25-hydroxyvitamin D₃ or other surgical treatments.

8. The level of serum calcium > 3.5 mmol/L or serum 25-hydroxyvitamin D₃ > 100 ng/mL.

Safety assessments Safety will be assessed by renal and liver function test, electrolyte, routine blood test, and serum 25-hydroxyvitamin D₃. Urine pregnancy test and serum 25-hydroxyvitamin D₃ level will be detected every three months. Other indicators are detected during the period of screening and after the treatment of every six months. Liver and urinary system ultrasound will be conducted after the treatment of 12 months and 24 months. The occurrence of any adverse events in trial participants will be recorded in the case report forms during each patient visit. We will withdraw patients who have severe adverse events, as it is unsafe for them to continue the trial. Meanwhile, we will give them relevant medical care and follow them up until the reaction has terminated.

Statistical analysis Statistical analyses will be performed using SPSS version 22.0 for Windows (SPSS Inc., Chicago, IL, USA). The randomisation sequence is generated by the use of the SPSS software. The normality of distribution of continuous variables are tested by one-sample Kolmogorov-Smirnov test. Continuous variables with normal distribution are reported as mean (standard deviation); non-normal variables are presented as median (interquartile range). Means of 2 and 3 or more continuous normally distributed variables, respectively, are compared by independent samples Student's t test or one-way ANOVA test. Mann-Whitney U test and Kruskal-Wallis test are used, respectively, to compare means of 2 and 3 or more groups of variables not normally distributed. The frequencies of categorical variables are compared using Pearson χ^2 or Fisher's exact test, when appropriate. A value of $P < 0.05$ is considered significant.

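### Scans are quarterly, but the listed tests take one value per woman and no rule covers withdrawn women, so the two-year effect may be understated

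*Combined protocol and SAP*

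**What the plan says.** Under Trial design the plan states "Gynecologic ultrasound examinations will be performed every three months", and Table 2 places the scans at months 0, 3, 6 and so on to 24. Study objectives gives the efficacy aim as "inhibiting the development of uterine fibroids in one year and two years". Outcomes measures defines the primary outcomes as "percent change in volume of the largest fibroid and total fibroids compared to baseline" and names no visit.

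For continuous variables, Statistical analysis says that means of normally distributed variables "are compared by independent samples Student's t test or one-way ANOVA test", and that otherwise "Mann-Whitney U test and Kruskal-Wallis test are used". The only other comparisons listed are for categorical frequencies. The section contains no repeated-measures model, no analysis population and no rule for a missing scan.

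The Withdrawal section lists eight grounds on which a woman must leave the study, not merely stop the supplement. The sixth is "Other medical or surgical treatments of uterine fibroids". No scans are provided for after withdrawal. The same event is counted among the secondary outcomes, so the plan expects it to happen. The only provision for withdrawal is the 10% allowance in Sample size.

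**The concern.** A two-group test on percent change at month 24 uses two of a woman's nine scans. If she left after month 15, the plan has no stated way to use the six scans already on file (months 0, 3, 6, 9, 12 and 15).

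This matters because one ground for leaving may be tied to the outcome. Exclusion criterion 1 keeps out women who already have symptoms or an indication for operation. A woman who needs fibroid treatment later has therefore probably changed since entry, and growth is a plausible reason. If vitamin D slows growth, more fast-growing fibroids would leave the control arms than the treated arms. The women remaining at month 24 would then look more alike than the groups really are. The trial is also open-label, so treatment decisions could differ between arms for reasons unrelated to efficacy.

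**Working it through.** **1. The plan's own figure.** 320 / 0.90 = 355.6, or 356 as 4 × 89. The plan rounds up to 360, or 90 per group, so the 10% step reproduces. The 320 itself could not be reproduced from the printed volumes under the readings tried, but nothing below depends on it. The allowance replaces the number of women lost. It does not restore the kind of woman lost.

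**2. Assumptions.** The documents give no growth rate, no SD of growth and no rate of fibroid treatment, so all of these are assumed. Log volume for woman *i* at time *t* (years) is a baseline plus *b_i·t* plus scan error, with *b_i* normal and SD 0.25 per year.
- Set-up A: control growth 30% over two years, vitamin D 0%, scan-error SD 0.15. After each follow-up visit the chance of leaving is 1/(1 + exp(−(a + β × log change so far))). β = 0 is no link to growth, 2 a weak link and 4 a strong link; *a* is set to give about 10% withdrawal on average.
- Set-up B: growth 0.25 (control) and 0.10 (vitamin D) per year on the log scale, scan-error SD 0.25. The true month-24 difference is 2 × (0.10 − 0.25) = −0.300. Withdrawal is wholly or partly driven by measured growth passing a threshold.
- Set-up C: as A, but with control growth 50%, β = 4 and 90 per arm.

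**3. Month-24 log difference, women with a month-24 scan only.** Shortfall = 1 − (completers / truth).

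| Set-up | Withdrawal, control vs vitamin D | Truth | Completers | Shortfall | All-visit model |
|---|---|---|---|---|---|
| A, no link | 9.9% vs 9.9% | −0.262 | −0.262 | 0% | not run |
| A, weak link | 11.2% vs 8.7% | −0.263 | −0.253 | 4% | not run |
| A, strong link | 12.5% vs 7.5% | −0.263 | −0.232 | 12% | not run |
| B, growth-driven | 7.5% vs 3.0% | −0.300 | −0.259 | 14% | −0.298 |
| B, growth-driven | 9.5% vs 6.0% | −0.300 | −0.264 | 12% | −0.297 |
| B, mostly unrelated | 10.0% vs 7.4% | −0.300 | −0.277 | 8% | not shown |
| B, mostly unrelated | 10.2% vs 8.8% | −0.300 | −0.285 | 5% | not shown |
| B, mostly unrelated | 7.8% vs 6.3% | −0.300 | −0.290 | 3% | not shown |
| C, strong link | 12.9% vs 5.8% | −0.408 | −0.364 | 11% | −0.408 |

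On the plan's own scale, mean percent change, set-up A gives −34.9 points against −32.1 for completers with the weak link (1 − 32.1/34.9 = 8%). With the strong link it gives −35.0 against −27.5 (1 − 27.5/35.0 = 21%).

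**4. Month 12.** In set-up B the month-12 shortfall was about 0-6%.

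**5. No true effect.** With the same withdrawal mechanism in both arms, the bias is about zero. With 30% growth in both arms but more withdrawal among controls (16.5% vs 7.6%), completers show a false difference of about 8 percentage points against vitamin D.

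**6. Carrying the last scan forward.** In a run of set-up A with the strong link (13.3% vs 8.1% withdrawal), the truth was −34.9 points, completers gave −27.3 and last value carried forward gave −30.6. The shortfalls are 1 − 27.3/34.9 = 22% and 1 − 30.6/34.9 = 12%, so the bias is reduced but not removed.

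**The case against.** A reader might infer that the plan drops withdrawn women and that its two-year result is therefore biased. The documents do not support that. Statistical analysis is silent on who is analysed, and a single-value test could be run on last values carried forward or repeated at each visit. None of the eight withdrawal grounds is growth. Several (own request, pregnancy, loss to follow-up, serum levels) have no stated tie to it. Entry is limited to fewer than four fibroids, with intramural fibroids of 1-4 cm, in women without an indication for operation, so fibroid treatment may be rare. When most withdrawal was made unrelated to growth, the shortfall fell to 3-8%. All of this stands, and it is why the point is worded as a possible bias.

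The remedy also has limits. The model recovers the truth in these simulations because withdrawal there depends only on recorded scans, which is the model's own assumption. Treatment decisions in an open-label trial may depend on symptoms or on knowing the arm. The model also targets growth as if the treatment had not been given, and the log scale yields ratios of geometric means rather than mean percent change. These are choices the plan would have to state. They do not remove the gap: with no rule in place, the handling of missing scans could be chosen after open-label data have been seen.

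**Conclusion.** The point holds as a risk that is cheap to remove. The plan collects nine scans, lists only one-value tests, requires withdrawal on an event plausibly linked to growth, and has no rule for the missing values. If withdrawn women are left out and vitamin D slows growth, the month-24 effect is roughly 5-20% too small at about 3-15% withdrawal per arm (individual runs: 3-22%). The month-12 effect is about 0-6% too small. If withdrawal is unrelated to growth, there is no bias. The sizes rest on assumed growth, variability and strength of the link, none of which the documents give.

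Two further inferences are tempting but unsupported. The first is to convert the month-24 shortfall into a loss from the planned 90% power. The sample size is built on 12-month volumes, where the bias is small. Losing fast growers also lowers the SD among completers, so the standardised effect falls by less than the raw one. The second is to expect a large precision gain from using all scans. That needs an effect proportional to time, which a model with visit as a category does not impose. With withdrawal unrelated to growth (about 10%, 90 per arm), the SDs of the estimates were similar: 0.084 for completers and 0.081 for the all-visit model.

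**What to change.** In Statistical analysis:
- Make the primary analysis a linear mixed model of log fibroid volume at all scheduled scans. Use visit as a category, group-by-visit terms, baseline constrained equal between arms (or entered as a covariate) and an unstructured covariance. Fit it for A vs B and for C vs D, for the largest fibroid and for total volume.
- Include every scan taken before withdrawal.
- Report the month-12 and month-24 contrasts back-transformed to percent change (ratio of geometric means) with 95% confidence intervals.
- State that the target is growth as if other fibroid treatment had not occurred.
- State a floor volume for fibroids no longer visible, since zero has no logarithm.
- Keep the single-visit test on percent change as a sensitivity analysis, and add one for withdrawal that depends on factors not recorded in the scans.

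The cost is SAP text and slightly more analysis work, with no new visits, data or patients and no change to the withdrawal rules. The downsides are a geometric-mean scale for the primary result and reliance on withdrawal being explained by recorded scans, which the added sensitivity analysis is there to test.

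### The 90% power claim is derived from absolute fibroid volume at 12 months, not from the percent-change primary outcomes, and the quoted volumes do not determine 320

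*Combined protocol and SAP*

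**What the plan says.** The Sample size paragraph rests on one earlier study. It gives a fibroid volume of 8.2 (2.1-30.5) cm³ "after the supplement of vitamin D 12 months and 11.4 (5.5-22.3") cm³ in controls. The 12-month label is attached to the supplemented arm and only implied for controls. The paragraph does not say whether these are volumes of the largest fibroid or of all fibroids, whether 8.2 and 11.4 are means or medians, or what the brackets are. With power 0.9 and α=0.05 it concludes: "one-sided), 320 participants will be required for the four groups and in a 1:1:1:1 ratio". That is 80 evaluable patients per group; 360 are to be enrolled to allow for 10% withdrawal.

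Outcomes measures defines the primary outcomes as "percent change in volume of the largest fibroid and total fibroids compared to baseline". Trial design names total volume only: "Percent change in volume of the total fibroids compared to baseline in different groups". Study objectives speaks of "inhibiting the development of uterine fibroids in one year and two years".

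Trial design randomises within vitamin D strata: patients in the lower stratum are "randomly assigned in a 1:1 ratio to intervention group A or control group B", and those in the upper stratum likewise to C or D. Statistical analysis lists tests by number of groups and by normality, for example "Mann-Whitney U test and Kruskal-Wallis test are used, respectively, to compare means of 2 and 3 or more groups", and closes with "A value of $P < 0.05$ is considered significant". It assigns no test to the primary outcomes and names no side.

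**The concern.** A power statement belongs to one outcome, at one time, for one contrast and one test. Here the outcome behind the calculation (volume in cm³ after treatment) differs from the outcome to be tested (percent change from each patient's own baseline). Post-treatment volume carries all the variation in fibroid size between patients. Percent change divides much of that out but adds the measurement error of two scans. Power for one could be higher or lower than for the other, and the documents give nothing to convert between them.

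At stake is how a null result is read. If the 90% is taken at face value, a non-significant difference in percent change will look like good evidence against an effect of the planned size, although no such size was ever stated for that outcome.

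**Working it through.** **Inputs from Sample size.** Power 0.90; α 0.05 one-sided; volumes 8.2 (2.1-30.5) and 11.4 (5.5-22.3) cm³; 320 evaluable in four equal groups, so 80 per group. No SD is given, so every SD below is an assumption about what the brackets mean.

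**Step 1. The dropout step.** 320/0.9 = 356, so 360 is sound.

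**Step 2. What 80 per arm implies.** n per arm = 2(1.645 + 1.282)²/d², so d = 2.926 × √(2/80) = 0.463.
- Raw scale: the difference is 11.4 − 8.2 = 3.2 cm³, so SD = 3.2/0.463 = 6.9 cm³.
- Log scale: the difference is ln(11.4/8.2) = 0.329, so SD = 0.329/0.463 = 0.71.

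If the strata are pooled (160 v 160), d = 0.327, and the implied SD is 9.8 cm³ or 1.01 on the log scale. None of these SDs appears in the documents.

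**Step 3. Can 80 per arm be recovered from the brackets?** Bracket widths are 28.4 and 16.8 cm³ (raw), or 2.676 and 1.400 (log). Root-mean-square SD over the two arms, one-sided 0.05:

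| Assumed meaning (divisor) | Scale | SD | n per arm for 90% | Power, 80 v 80 |
|---|---|---|---|---|
| Interquartile range (1.349) | raw | 17.3 | 501 | 32% |
| Interquartile range (1.349) | log | 1.58 | 396 | 37% |
| 95% spread of patients (3.92) | raw | 5.95 | 60 | 96% |
| 95% spread of patients (3.92) | log | 0.54 | 47 | 98.5% |
| Range (4) | raw | 5.83 | 57 | 96.5% |
| Range (4) | log | 0.53 | 45 | 99% |

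At 160 v 160 the interquartile reading gives 50% (raw) or 58% (log). A simulated Mann-Whitney test on log-normal data gave 37% at 80 v 80, the same as the log-scale row. If the brackets were confidence intervals, the SD would depend on the size of the previous study, which is not given, so no figure follows.

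Some combinations do land near the plan's number. The wider arm's SD used for both arms, with divisor 4 or 3.92, gives 71-88 per arm. Divisor 3.29 (a 90% spread) with the average raw SD gives 79. The bracket read as ±1 SD gives 78 with the control arm's log SD, or 164 per pooled arm with the average log SD. No text supports any of these over the others.

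**Step 4. Sidedness.** ANOVA and Kruskal-Wallis have no one-sided form, so the planned one-sided α can apply only to a two-group test. If a two-sided 0.05 test is used at d = 0.463, power at 80 v 80 is about 83%, and 90% would need 2(1.960 + 1.282)²/0.463² ≈ 99 per arm. The same 83% applies to a pooled contrast at its own implied d of 0.327.

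**Step 5. What the planned numbers can detect for percent change.** In SD units, for a t test at 90% power: 0.463 one-sided or 0.513 two-sided at 80 v 80; 0.327 or 0.362 at 160 v 160. Multiplying by an assumed SD of percent change gives percentage points:

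| Assumed SD (points) | 80 v 80, one-sided | 80 v 80, two-sided | 160 v 160, one-sided | 160 v 160, two-sided |
|---|---|---|---|---|
| 40 | 19 | 21 | 13 | 14 |
| 60 | 28 | 31 | 20 | 22 |
| 80 | 37 | 41 | 26 | 29 |

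**The case against.** Several points on the other side stand.

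- **320 may be a correct calculation.** Planning on the larger SD is a common conservative choice, and it gives values close to 80 per arm. A reader might infer from the interquartile row that the number is an arithmetic error. The documents do not support that: they never label the brackets, and the median (interquartile range) convention in Statistical analysis governs this trial's reporting, not the previous study's. The figure is undetermined, not disproved.
- **Raw-scale SDs fit poorly.** Both brackets are nearly symmetric on the log scale and skewed on the raw scale, so turning raw widths into SDs by normal theory is rough. The log rows avoid this, and they show the same spread of answers.
- **The contrast may be pooled.** Trial design makes 80 v 80 the natural reading, but Sample size does not say so. Pooling raises the interquartile figures to 50-58%, still far from 90%.
- **Sidedness is not contradicted.** Sample size says one-sided; Statistical analysis is silent. The 83% is conditional on a two-sided test, which the plan does not state.

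One argument does not stand: that absolute volume is an adequate proxy. It could serve only with a stated conversion to percent change, including an SD, and none is given.

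**Conclusion.** The mismatch is plain on the text: the 90% belongs to absolute volume at 12 months, and the trial will test percent change in two volumes under an objective that covers one and two years. With no difference or SD for percent change, the stated power is unsupported for the primary outcomes. High confidence attaches to this and to the missing inputs.

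The size of the gap cannot be given as one number. For absolute volume at 80 v 80, one-sided, the readings tabulated run from 32-37% to 96-99%, all resting on assumed meanings of the brackets. For percent change, power cannot be computed from the documents.

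A reader might go further and conclude that the trial is underpowered. That does not follow, since power for percent change could be above or below 90%. This is an endpoint mismatch and an undocumented calculation. It should be fixed, but it does not show that the trial cannot answer its question.

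**What to change.** Withdraw the 90% claim based on absolute volume and rewrite the Sample size paragraph so that it:

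1. states power for percent change in a named volume (largest or total) at a named time point;
2. names the contrast (A v B and C v D, or strata pooled) and the test;
3. uses one sidedness, stated identically in Sample size and Statistical analysis;
4. labels any previous-study figures that are kept, and gives the SD and scale used;
5. states what the planned numbers can detect, in percentage points under an explicitly assumed SD.

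Possible wording, if two-sided testing within strata is chosen: with 80 evaluable patients per arm, the trial has 90% power at two-sided 0.05 (t test) to detect a difference of 0.51 SD in percent change, about 31 percentage points if the SD is 60 points. The one-sided equivalent is 0.46 SD, about 28 points. Pooled, the figures are 0.36 SD two-sided and 0.33 SD one-sided. A Mann-Whitney test would give somewhat different values. The SD of 60 is only an example; the investigators should justify their own or show a range.

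Cost: one paragraph rewritten, and the test and side added to Statistical analysis. The planned 360 need not change to make the statement accurate. The downside is that the stated power may be less favourable than 90%.

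### The sample size assumes a one-sided 5% test, but the analysis rule gives no sidedness; if the primary tests are two-sided, a true 90% power would be about 83%

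*Combined protocol and SAP*

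**What the plan says.** The Sample size section cites fibroid volumes from an earlier study, "8.2 (2.1-30.5) cm³ after the supplement of vitamin D 12 months and 11.4 (5.5-22.3) cm³ in the control group". It then sets the power: "On the basis of a 0.9 power to detect a significant difference". The alpha is 0.05 and the test is described as "one-sided), 320 participants will be required for the four groups and in a 1:1:1:1 ratio". Four equal groups make 80 evaluable per group. The enrolment target follows: "Allowing for a 10% withdrawal rate, we plan to include 360 patients in the whole trial", which is 90 per group.

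The Statistical analysis section assigns tests by number of groups and by distribution: t test or Mann-Whitney for two groups, one-way ANOVA or Kruskal-Wallis for three or more, and Pearson chi-square or Fisher's exact test for categorical data. One rule covers them all: "A value of $P < 0.05$ is considered significant". It says neither one-sided nor two-sided, and no other section does so for the analysis.

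Under Trial design, A is randomised against B and C against D, so the natural primary contrasts are two-group comparisons. Under Outcomes measures, the primary outcome is percentage change in fibroid volume from baseline, not the volume itself.

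**The concern.** A power statement belongs to one particular test. Here the planning test is one-sided at 5%, while the decision rule is a bare P < 0.05. Without a stated direction, most readers and most software output will treat that as two-sided. The 90% would then describe a more lenient test than the one used.

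The silence also leaves a choice open. In an open-label trial, whether to report a one-sided or a two-sided P value could be settled after the data are seen. If P values are halved to match the planning, the chance of a false claim of benefit is 5% per comparison, against 2.5% in that direction for a two-sided 5% test.

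**Working it through.** **Inputs.** From Sample size: alpha 0.05 one-sided, power 0.90, 320 evaluable in four equal groups (80 each), 10% withdrawal, 360 enrolled (90 each). From Statistical analysis: P < 0.05, sidedness not stated. Normal quantiles: z(0.95) = 1.645, z(0.90) = 1.282, z(0.975) = 1.960.

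**1. Can the plan's 320 be reproduced?** For two means, n per group = 2 × (1.645 + 1.282)² / d² = 17.13 / d², where d is the difference in SD units. The brackets around the volumes are not labelled, and no SD is given, so several readings were tried.

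- *Median and interquartile range, raw scale (assumed).* SDs are (30.5 − 2.1)/1.349 = 21.05 and (22.3 − 5.5)/1.349 = 12.45, pooled 17.30. d = (11.4 − 8.2)/17.30 = 0.185, so n = 501 per group.
- *The same on the log scale.* The difference is ln(11.4/8.2) = 0.330. SDs are ln(30.5/2.1)/1.349 = 1.984 and ln(22.3/5.5)/1.349 = 1.038, pooled 1.583. d = 0.208, so n = 396 per group.
- *Brackets read as ranges (width/4 or width/6) or as 95% limits (width/3.92), pooled SD.* n = 20 to 60 per group.
- *Nearest to 80.* 85 per group, using only the treated arm's bracket as a range/4. A value of 319 does arise from the control arm's interquartile SD, but it is per group and two-sided, so it is not the stated calculation.

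The 320 is not reproduced. The withdrawal step is acceptable: 320/0.9 = 356, and 360 is close to that.

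**2. Power if the stated design is taken at face value but tested two-sided.** Power of 90% one-sided at 5% means that the expected difference is 1.645 + 1.282 = 2.926 standard errors (from unrounded quantiles). Two-sided at 0.05:

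- Power = Φ(2.926 − 1.960) = Φ(0.966) = 83.3%. The noncentral t gives 83.2%.

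This step uses only the stated alpha and power. It is the same whether the sized contrast is 80 versus 80 or a pooled 160 versus 160.

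**3. Other numbers analysed.** At 80 per group the implied effect is d = 2.926 × √(2/80) = 0.463 SD. Two-sided power is Φ(0.463 × √(n/2) − 1.960):

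| Evaluable per group | Source | Two-sided power |
|---|---|---|
| 80 | 320/4 | 83% |
| 81 | 90 × 0.9 | 84% |
| 90 | no withdrawals | 87% |

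**4. Size needed to keep 90% two-sided at that effect.** The ratio is (1.960 + 1.282)² / 2.926² = 1.227. Then 80 × 1.227 = 98.2, rounded up to 99 per group: 396 evaluable, or 396/0.9 = 440 enrolled.

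**5. How far the 83% can be trusted.** With d from step 1 in place of the implied 0.463, two-sided power at 80 per group is 22% (raw) or 26% (log) under the interquartile reading, and above 92% under the pooled range or 95%-limit readings. The 83% is tied to an effect that the plan does not state.

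**The case against.** The strongest reply is that the documents contain an omission, not two conflicting rules. The only statement on sidedness anywhere is the one-sided one in Sample size. If it is carried into the analysis, the stated 90% and 320 are unaffected. This stands: two-sided testing is inferred from convention and from silence. A reader might infer that the plan specifies a two-sided test and that its power has therefore fallen to 83%. The documents do not say that.

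A reader might also infer that the listed tests rule out a one-sided analysis. ANOVA and Kruskal-Wallis with three or more groups have no direction, and Pearson chi-square as written has none. But the A versus B and C versus D contrasts would use the t test or Mann-Whitney, and both have one-sided forms. The argument does not reach the primary comparison.

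Third, 83% might be taken as the power to detect 8.2 versus 11.4 cm³. It is not. Neither 90% nor 83% can be recovered from those volumes, and they are not on the percentage-change scale of the primary outcome.

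Finally, declaring a one-sided analysis would also remove the mismatch. That is true, and the choice is the sponsor's. What the reply does not answer is that the analysis section says neither, so the power statement is not tied to a defined test.

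**Conclusion.** The point holds in conditional form. The trial is sized with a one-sided 5% test, and the analysis rule does not say that this is the test to be used. On the ordinary two-sided reading, the nominal loss is about 7 percentage points, from 90% to 83%.

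This rests on three assumptions: that P < 0.05 is applied two-sided; that the stated 90% at 80 evaluable per group is correct; and that the true effect is therefore about 0.46 SD. The first is an inference from silence. The second and third cannot be verified from the plan. The mismatch depends on none of the volume figures and remains however the 320 was obtained. The power loss is moderate, but it should be corrected before analysis.

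**What to change.** - **Statistical analysis:** state that the primary A versus B and C versus D comparisons are two-sided at 0.05.
- **Sample size:** amend the sentence so that it no longer claims 90% power for that test. Give the assumed difference and SD, on the percentage-change scale of the primary outcome, that yield 80 per group. Until these are given, report about 83% only as conditional on the stated design being correct, not as verified power for the quoted volumes.
- **If the sponsor keeps a one-sided 5% test:** Statistical analysis must say so in advance, name the direction, and acknowledge a 5% (not 2.5%) chance of a false claim of benefit per comparison. The 90% and 320 then need no change on this account, although the effect and SD behind them are still missing.

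The cost is a short edit in two sections, plus recovery of the assumptions behind the 320. No patients are added. With the two-sided choice, the stated power becomes less favourable; restoring 90% at the implied effect would instead mean 396 evaluable (440 enrolled), which this fix does not require.
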